4.2.2 Restrictions

4.2.2.1 Restrictions regarding concomitant treatment

The following treatments should not be taken with dabigatran:

Proprietary confidential information.

© 2019 Boehringer Ingelheim International GmbH or one or more of its affiliated companies. All rights reserved.

This document may not - in full or in part - be passed on, reproduced, published or otherwise used without prior written permission.

- All VKAs
- Therapeutic unfractionated heparin or LMWH (heparin flushes of indwelling catheters is allowed) or fondaparinux
- Fibrinolytic agents (tissue plasminogen activators (t-PA) e.g. alteplase, or any other thrombolytic agents to re-establish patency of obstructed central venous line are allowed as long as the used dose is devoid of relevant systemic effects)
Note: Additionally fibrinolytic agents should not be taken within 48 hours prior to dabigatran administration.
- P-glycoprotein inhibitors including but not limited to: Amiodarone, Cyclosporine, Dronedarone, Itraconazole, Ketoconazole, Nelfinavir, Quinidine, Ritonavir, Saquinavir, Tacrolimus, Verapamil
- P-glycoprotein inducers including but not limited to: Rifampicin, St. John's Wort, Carbamazepine, Phenytoin
Note: Additionally P-glycoprotein inducers should not be taken within one week prior to dabigatran administration.
- Asparaginase - one week wash-out period to be considered (two weeks in case of PEG- Asparaginase)
- Any other investigational drug (with the exception of the specific reversal agent to counteract the antithrombotic activity of dabigatran etexilate where the patient is eligible to participate in a specific trial in a framework of clinical investigation)

Note: Intended extended use of anti-inflammatory agents or agents containing ASA should be avoided. Corticosteroids in general should be excluded but may be included if they are part of a chemotherapy regimen given in cycles, or if the benefits of corticosteroid therapy clearly outweigh risks.

4.2.2.2 Restrictions on diet and life style

Dabigatran etexilate may be taken with or without food. For more details please refer to [Section 4.1.4](#).

SOC restrictions should be followed based on locally approved product labels.

4.3 TREATMENT COMPLIANCE

Subjects or, if applicable, parents or legal guardians, will be asked to carefully complete a daily medication intake log for dabigatran or SOC. Subjects / parents / legal guardians will be asked to bring this completed log to every clinic visit which they will attend. Empty dabigatran capsule containers or solution vials or any unused drug should also be returned to the investigator's site for disposal and compliance calculation. Compliance should be calculated using the below equation preferably based on the returned medication (completed logs may also be used):

Compliance (in %) = (Actual number of dabigatran doses taken since last count / Planned number of dabigatran doses which should have been taken in the same period) x 100

Proprietary confidential information.

© 2019 Boehringer Ingelheim International GmbH or one or more of its affiliated companies. All rights reserved.

This document may not - in full or in part - be passed on, reproduced, published or otherwise used without prior written permission.

If an interruption of SOC or dabigatran etexilate was medically required this would be considered by reducing the number of expected doses that “should have been taken” accordingly in the compliance calculation.

Unreliable subjects should not be entered in the study at the discretion of the investigator. Compliance during the treatment period should be between 80% and 120%. In cases where compliance is not achieved based on the above definition, the parent or legal guardian and when applicable the patient should be interviewed and re-informed about the purpose and the conduct of the trial and the importance to maintain good compliance. If non-compliance persists despite all possible efforts, patients should be removed from the allocated treatment and alternative therapy should be proposed in such cases.

Proprietary confidential information.

© 2019 Boehringer Ingelheim International GmbH or one or more of its affiliated companies. All rights reserved.

This document may not - in full or in part - be passed on, reproduced, published or otherwise used without prior written permission.

5. VARIABLES AND THEIR ASSESSMENT

5.1 EFFICACY - PHARMACODYNAMICS

5.1.1 Endpoints of efficacy

Primary endpoint:

Efficacy combined endpoint Proportion of patients with:

- Complete thrombus resolution and;
- Freedom from recurrent VTE (including symptomatic and asymptomatic, contiguous progression or non-contiguous new thrombus, deep vein thrombosis, pulmonary and paradoxical embolism, thrombus progression) and;
- Freedom from mortality related to VTE.

The events outlined in the above combined primary endpoint will be assessed by radiologists or other such qualified clinicians using an appropriate method such as ultrasound, echocardiography, venography or computed tomography (CT scan) based on the location of the thrombus and the test used to perform the baseline assessment.

All components of the primary efficacy endpoint as well as all bleeding and all fatal events will be centrally adjudicated by an independent blinded committee.

Secondary endpoints:

- Freedom from major bleeding events (MBEs), defined as either fatal bleeding; clinically overt bleeding associated with a decrease in haemoglobin of at least 20 g/L in a 24-hour period; bleeding that is retroperitoneal, pulmonary, intracranial or otherwise involves the central nervous system; or bleeding that requires intervention in an operating suite.
- Pharmacokinetic and pharmacodynamic assessments at visit 3 (after at least six consecutive dabigatran doses) and after at least 3 days following any dabigatran dose adjustment
- Frequency of dose adjustments (i.e. Number of subjects with dose adjustment), temporary and permanent discontinuation from therapy and number of subjects with laboratory monitoring requirements for dose adjustment during the treatment phase
- Frequency of switch of type of anti-coagulation therapy (including dabigatran to SOC) (Frequency of subjects switching the type of anti-coagulation therapy including dabigatran etexilate to standard of care and switching from an intended standard of care treatment to another)
- Freedom from thrombus progression at end of therapy (day 84 after randomisation (Visit 8) or eEOT whichever comes first) compared to baseline
- Assessment of the acceptability of an age-appropriate formulation at end of therapy
- All bleeding events

Proprietary confidential information.

© 2019 Boehringer Ingelheim International GmbH or one or more of its affiliated companies. All rights reserved.

This document may not - in full or in part - be passed on, reproduced, published or otherwise used without prior written permission.

- All-cause mortality
- All components of the primary efficacy endpoints

5.1.2 Assessment of efficacy

5.1.2.1 Physical examination

A complete physical examination will be completed for all patients at the time points noted in the [Flow Chart](#). All abnormal findings at the screening visit will be recorded on the Medical History/Baseline Conditions eCRF page. New abnormal findings or worsening of baseline conditions detected at follow-up physical examinations will be recorded as AEs on the appropriate eCRF page, if judged clinically relevant by the investigator. A complete physical examination should be done when a patient discontinues the trial prematurely. In the event that clinically relevant findings are observed during the physical examination at the end of the study (or at early withdrawal from the trial), the patient should be followed by the investigator until resolution of the event, or an agreement has been made with the sponsor that follow-up is sufficient on that patient.

5.1.2.2 Venous thromboembolism assessment

In case of suspected VTE, the event should be evaluated using appropriate imaging modalities per local guidelines or as required per investigator judgment. Example of appropriate evaluations methods are listed below.

- Suspected DVT: Venous compression ultrasonography (CUS) or venography
- Suspected PE: Ventilation-perfusion (V-Q) lung scan, pulmonary angiography or spiral (helical) CT
- Suspected PTS: An appropriate instrument (e.g. the Manco-Johnson Instrument or Villalta scale or a similar instrument; the chosen instrument will be available in the ISF)
- Suspected paradoxical embolism (PDE): CT / MR angiography or other appropriate evaluation

The final assessment (at end of therapy) of the resolution status of the thrombus must be done using the same method as the baseline evaluation when appropriate.

Proprietary confidential information.

© 2019 Boehringer Ingelheim International GmbH or one or more of its affiliated companies. All rights reserved.

This document may not - in full or in part - be passed on, reproduced, published or otherwise used without prior written permission.

Note: If clinical evaluations warrant imaging (e.g. suspected thrombus extension), then per investigator judgment, appropriate imaging may be performed. When feasible, a baseline radiological assessment (e.g. CT) may be supplemented with an acceptable non-radiological assessment (e.g. MRI) at baseline which could then be repeated at the end of therapy (study day 84 (visit 8) or eEOT, whichever comes first) hence alleviating any potential unwarranted radiation exposure.

5.1.2.3 Bleeding assessment

Patients will be carefully assessed for signs and symptoms of bleeding.

The following definitions for bleeding are based on recommendations made by the Perinatal and Paediatric Haemostasis Subcommittee during the 56th-58th Scientific and Standardization Committee (SSC) Meetings of the ISTH ([R11-4225](#)).

Major bleeding:

- Fatal Bleeding
- Clinically overt bleeding associated with a decrease in haemoglobin of at least 2 g/dL (20 g/L) in a 24 hour period
- Bleeding that is retroperitoneal, pulmonary, intracranial, or otherwise involves the central nervous system
- Bleeding that requires surgical intervention in an operating suite

Clinically relevant non-major (CRNM) bleeding:

- Overt bleeding for which a blood product is administered and which is not directly attributable to the patient's underlying medical condition
- Bleeding that requires medical or surgical intervention to restore haemostasis, other than in an operating suite

Minor bleeding:

- Minor bleeds are any overt or macroscopic evidence of bleeding that does not fulfil the criteria for either major bleeding or clinically relevant, non-major bleeding

5.2 SAFETY

5.2.1 Endpoints of safety

The main safety endpoint, freedom from major bleeding events (MBEs), is defined as either fatal bleeding; clinically overt bleeding associated with a decrease in haemoglobin of at least 20 g/L in a 24-hour period; bleeding that is retroperitoneal, pulmonary, intracranial or otherwise involves the central nervous system; or bleeding that requires intervention in an operating suite.

Other safety endpoints:

Proprietary confidential information.

© 2019 Boehringer Ingelheim International GmbH or one or more of its affiliated companies. All rights reserved.

This document may not - in full or in part - be passed on, reproduced, published or otherwise used without prior written permission.

- Incidence of bleeding events including:
 - Major bleeding events; clinically relevant non-major bleeding events (CRNM), minor bleeding events and any bleeding events
 - Combined endpoint of major and CRNM bleeding events
- Incidence of adverse events, protocol-specified AESI and serious adverse events
- Treatment discontinuation due to an adverse event
- Change from baseline in safety laboratory values, vital signs and physical examination
- Global assessment of tolerability (measured as treatment discontinuation and adherence) to study medication

5.2.2 Assessment of adverse events

5.2.2.1 Definitions of adverse events

Adverse event

An adverse event (AE) is defined as any untoward medical occurrence, including an exacerbation of a pre-existing condition, in a patient in a clinical investigation who received a pharmaceutical product. The event does not necessarily have to have a causal relationship with this treatment.

Serious adverse event

A serious adverse event (SAE) is defined as any AE which results in death, is immediately life-threatening, results in persistent or significant disability / incapacity, requires or prolongs patient hospitalisation, is a congenital anomaly / birth defect, or is to be deemed serious for any other reason if it is an important medical event when based upon appropriate medical judgment which may jeopardise the patient and may require medical or surgical intervention to prevent one of the other outcomes listed in the above definitions.

Intensity of adverse event

The intensity of the AE should be judged based on the following:

- | | |
|-----------|--|
| Mild: | Awareness of sign(s) or symptom(s) which is/are easily tolerated |
| Moderate: | Enough discomfort to cause interference with usual activity |
| Severe: | Incapacitating or causing inability to work or to perform usual activities |

Proprietary confidential information.

© 2019 Boehringer Ingelheim International GmbH or one or more of its affiliated companies. All rights reserved.

This document may not - in full or in part - be passed on, reproduced, published or otherwise used without prior written permission.

Causal relationship of adverse event

Medical judgment should be used to determine the relationship, considering all relevant factors, including pattern of reaction, temporal relationship, de-challenge or re-challenge, confounding factors such as concomitant medication, concomitant diseases and relevant history. Assessment of causal relationship should be recorded in the case report forms.

Yes: There is a reasonable causal relationship between the investigational product administered and the AE.

No: There is no reasonable causal relationship between the investigational product administered and the AE.

Worsening of the underlying disease or other pre-existing conditions

Worsening of the underlying disease or of other pre-existing conditions will be recorded as an (S)AE in the (e)CRF.

Changes in vital signs, ECG, physical examination, and laboratory test results

Changes in vital signs, ECG, physical examination and laboratory test results will be recorded as an (S)AE in the (e)CRF, if they are judged clinically relevant by the investigator.

Protocol-specified Adverse Events of Special Interest (AESI)

The following are considered as Protocol-specified AESI:

- Hepatic injury defined by the following alterations of liver parameters: An elevation of AST and/or ALT ≥ 3 fold ULN combined with an elevation of total bilirubin ≥ 2 fold ULN measured in the same blood draw sample.

Patients showing these lab abnormalities need to be followed up according to [Appendix 10.2](#) of this clinical trial protocol and the “DILI checklist” provided in ISF.

- Creatinine value shows a ≥ 2 -fold increase from baseline and is above the upper limit of normal.

Protocol-specified AESI are to be reported in an expedited manner similar to Serious Adverse Events, even if they do not meet any of the seriousness criteria – for details please see chapter 5.2.2.2.

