- In the opinion of the Investigator, continuation in the trial is not in the patient's best interest. If treatment non-compliance persists despite all possible efforts, patients should be removed from the allocated treatment and alternative therapy should be proposed in such cases.
- If a patient becomes pregnant or a pregnancy is suspected during the trial the investigational drug (dabigatran) will be stopped, the patient will be discontinued from the dabigatran treatment arm and will be put on an appropriate SOC therapy per investigator judgment. The patient will be followed up until the end of the study and until the birth or otherwise termination of the pregnancy. For further information, including the process for follow-up on the outcome of the pregnancy, please see [Section 5.2.2.2](#).
- If a patient develops an active meningitis, encephalitis, or intracranial abscess.
- If a patient develops renal dysfunction anytime during the course of the study (eGFR < 50 mL/min/1.73m² using the Schwartz formula, confirmed by one retesting within 14 calendar days), treatment with dabigatran must be stopped and the patient must be switched to an appropriate SOC regimen.
If a patient develops eGFR < 50 mL/min/1.73m² using the Schwartz formula for

Proprietary confidential information.

© 2019 Boehringer Ingelheim International GmbH or one or more of its affiliated companies. All rights reserved.

This document may not - in full or in part - be passed on, reproduced, published or otherwise used without prior written permission.

second time during the course of the study, treatment with dabigatran etexilate (when applicable) must be stopped without further retesting and the patient must be switched to an appropriate SOC regimen.

- The patient does not require treatment with anticoagulants any longer due to a complete thrombus resolution as confirmed by appropriate imaging modalities prior to 12 weeks of planned anticoagulation treatment. In such cases, an early EOT visit is to be performed and the patient should still be followed up according to the remaining visit schedule until the end of the study.

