- Total Daily dose: A specific volume of a 6.25 mg/mL solution after reconstitution is administered (BID) based on an age and weight adjusted nomogram included in [Appendix 10.3.1](#). This nomogram has been generated to estimate a yield and exposure comparable to the exposure observed in previously completed adult VTet/sVTEp and AF populations, particularly in patients whose observed exposure was generally associated with the most favourable balance between efficacy and safety.
- Route of administration: p.o.
- List of excipients: The most up to date list will be provided in the ISF

The active comparator (e.g. LMWHs or VKAs or fondaparinux used as SOC) will not be supplied as part of the investigational medicinal product.

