5.2.2.2 Adverse event and serious adverse event reporting

All adverse events, serious and non-serious, occurring during the course of the clinical trial (i.e., from signing the informed consent onwards through the follow-up period) will be collected, documented and reported to the sponsor by the investigator on the appropriate CRF(s) / eCRFs / SAE reporting forms. Reporting will be done according to the specific

Proprietary confidential information.

© 2019 Boehringer Ingelheim International GmbH or one or more of its affiliated companies. All rights reserved.

This document may not - in full or in part - be passed on, reproduced, published or otherwise used without prior written permission.

definitions and instructions detailed in the ‘Adverse Event Reporting’ section of the Investigator Site File.

The end of residual effect period (REP) for dabigatran etexilate and SOC is set at 6 days after last drug administration. Therefore all events reported within 6 days of the last trial medication will be considered on treatment. All adverse events will be reported up until the end of the follow-up period, which is approximately 16 weeks after randomization.

Post Study:

The investigator may report SAEs which occurred in a subject after the end of the follow-up period, if the investigator becomes aware of them.

For each adverse event, the investigator will provide the onset date, end date, intensity, treatment required, outcome, seriousness, and action taken with the investigational drug. The investigator will determine the relationship of the investigational drug to all AEs as defined in [Section 5.2.2.1](#).

The investigator must report the following events using paper process SAE form via telephone/fax immediately (within 24 hours or the next business day whichever is shorter) to the sponsor: SAEs, AESIs and non-serious AEs relevant to the SAE and/or AESI.

BI has set up a list of AEs which are defined to be always serious. In order to support the investigator with the identification of these “always serious adverse events”, if a non serious AE is identified to be serious per BI definition, a query will be raised. The investigator must verify the description and seriousness of the event. If the event description is correct, the item “serious” needs to be ticked and an SAE has to be reported in expedited fashion following the same procedure as above.

The list of these adverse events can be found via RDC.

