7.3.3 Safety analyses

Major bleeding events will be analysed as a secondary endpoint. All bleeding events and combined endpoint of major and clinical-relevant bleeding events will be analysed by the Cox proportional hazards model with treatment being the factor and stratified by age group if appropriate. Pooling of age groups or non-stratified analysis might be performed if the event rate is low. All safety analyses as well as all bleeding events and all-cause mortality analysed as efficacy endpoints will be performed on the treated set.

The safety analysis set will include all randomized patients who take at least one dose of study medication. Patients in the safety population will be analysed according to the study treatment they have received. The safety analyses will be descriptive in nature and will be based on BI standards. The safety analyses will include the following parameters:

- All AEs
- protocol-specified AESI
- serious AEs
- AEs leading to treatment discontinuation

AEs will be coded using the MedDRA dictionary. All AEs will be classified according to the following trial periods: screening, on-treatment, post treatment. All AEs with an onset date/time after the 1st dose of trial medication up to 6 days after the last intake of study medication will be assigned to the treatment period for evaluation. In addition, AEs with onset date before start of the trial treatment but with worsening in intensity during the treatment will also be assigned to the on-treatment period. Other AEs will be assigned to the screening or post-treatment period, respectively. All AEs (including bleeding) in the treatment period will be tabulated in total and according to seriousness, severity and possible relationship to trial medication. AEs in the screening or follow-up period will be listed.

Other lab data, vital signs, physical examinations data and ECG data will be reported descriptively.

Proprietary confidential information.

© 2019 Boehringer Ingelheim International GmbH or one or more of its affiliated companies. All rights reserved.

This document may not - in full or in part - be passed on, reproduced, published or otherwise used without prior written permission.

Proprietary confidential information.

© 2019 Boehringer Ingelheim International GmbH or one or more of its affiliated companies. All rights reserved.

This document may not - in full or in part - be passed on, reproduced, published or otherwise used without prior written permission.

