All AEs (including bleeding) in the on-treatment period will be tabulated. AEs occurring outside the on-treatment period will be summarized in listings only and assigned to ‘screening’, ‘post-treatment’, or ‘post-study’.

According to ICH E3 (5), AEs classified as ‘other significant’ will include those non-serious and non-significant AEs with

- (i) ‘action taken = discontinued’ or ‘action taken = reduced’, or
- (ii) marked haematological and other lab abnormalities or lead to significant concomitant therapy as identified by the Clinical Trial Leader/Investigator at a Medical Quality Review Meeting.

An overall summary of AEs will be presented.

Frequency of patients with AEs will be summarised by age group, treatment, primary system organ class and preferred term. Separate tables will be provided for patients with other significant AEs according to ICH E3 (5), for patients with serious adverse events (SAEs), protocol-specified adverse events of special interest (AESIs), for patients with drug related AEs, as well as patients with AEs leading to treatment discontinuation and death. The system organ classes and preferred terms will be sorted by descending order of frequency.

The following are considered as protocol-specified AESI:

- Hepatic injury defined by the following alterations of liver parameters: An elevation of AST and/or ALT ≥ 3 fold ULN combined with an elevation of total bilirubin ≥ 2 fold ULN measured in the same blood draw sample.
- Creatinine value shows a ≥ 2 fold increase from baseline and is above the upper limit of normal.

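### Protocol 5.2.2 ties AE causality and action taken to dabigatran, while the AE tables are planned for both arms and the SAP leaves drug-related undefined

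*Protocol*

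**What the plan says.** **Collection.** Protocol 5.2.2.1 gives a single Yes/No causality rule. Yes means "There is a reasonable causal relationship between the investigational product administered and the AE", and "Assessment of causal relationship should be recorded in the case report forms". Protocol 5.2.2.2 adds that "The investigator will determine the relationship of the investigational drug to all AEs", referring back to 5.2.2.1, and lists among the items for each AE the "action taken with the investigational drug".

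**Meaning of the terms.** The title page and Protocol 4.1.1 name dabigatran etexilate as the investigational product. Protocol 3.3.4.1 states, for pregnancy, that "the investigational drug (dabigatran) will be stopped". Protocol 4.1.1 says the active comparators "will not be supplied as part of the investigational medicinal product".

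**Analysis.** Protocol 7.3.3 tabulates on-treatment AEs "according to seriousness, severity and possible relationship to trial medication". Protocol 3.1, in setting the residual effect period, takes trial medication to be dabigatran and SOC. SAP 7.8.1 summarises AEs by treatment and plans separate tables, including one "for patients with drug related AEs" and one for other significant AEs. One criterion for that last category is that the action taken was discontinuation or reduction. The SAP does not say which drug either item refers to.

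**Regulatory reporting.** Protocol 8.4.1 names the EU product characteristics as the listedness reference for SOC.

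**The concern.** The tables compare two arms, but the rule that supplies their data is worded for the drug given in one of them. If sites follow the wording, an event caused by a heparin, a vitamin K antagonist or fondaparinux is recorded as unrelated, while a comparable event on dabigatran can be recorded as related. The related-AE comparison would then differ between arms because of how the question is put. If some sites answer for SOC and others do not, the SOC column mixes two definitions. The trial is open-label and safety relative to SOC is a main objective (Protocol 2.2), so readers are likely to look at this table.

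**Working it through.** The plan gives no figure on this point, so the check is textual.

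1. **Could the terms simply mean assigned treatment?** Protocol 5.2.2.2 names dabigatran etexilate and SOC together, and speaks of trial medication, when it sets the 6-day residual effect period. A few lines later it uses investigational drug for relationship and action taken. The section therefore has a term covering both arms and does not use it for these two items. In the SAP, deviation code Z3 (Table 6.2: 1) likewise ties drug-related events to failure to stop dabigatran.

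2. **Is there any instruction to assess SOC?** Neither document expressly tells the investigator to record causality or action taken for an SOC drug.

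3. **Three cases under the literal wording:**
   - *SOC-arm patient, AE caused by the SOC drug.* No investigational product was given, so relationship is No and action taken has no referent. The AE is still counted in the all-AE table.
   - *Dabigatran-arm patient, comparable AE caused by dabigatran.* Relationship is Yes and action taken applies.
   - *Patient switched from dabigatran to SOC, AE starting more than 6 days after the last dabigatran dose and within 6 days of the last SOC dose.* SAP 7.8.1 assigns the AE to the SOC on-treatment period, but the causality question still concerns dabigatran. The column and the question then refer to different drugs.

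4. **Which outputs depend on each item?**
   - *Relationship* feeds the drug-related AE table only.
   - *Action taken* feeds the first criterion for other significant AEs, and possibly the table of AEs leading to discontinuation, whose source field is not stated. It does not feed the drug-related table.
   - *Neither item* feeds the primary endpoint, the adjudicated bleeding analyses (Protocol 7.3.2, SAP 7.5.2), or the tables of all AEs, SAEs and AEs of special interest.

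5. **Bounds.** If the case report form asks about the medication received, no SOC-related AE is misclassified. If it asks about dabigatran alone and sites comply, all of them are. The documents do not say which.

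**The case against.** The strongest reply is that the protocol plainly intends SOC to be assessed and that investigational product is template wording for the treatment given. Protocol 7.3.3 uses trial medication, 8.4.1 treats SOC as a possible suspect drug, 5.2.2.2 requires a relationship judgement for every AE in both arms, and SAP 6.1 defines trial treatment as either drug. The causality field is in the case report form, and further AE instructions are in the Investigator Site File. Either may already ask about SOC. Protocol 4.1.1 is also about supply, so its sentence on comparators is weak evidence about causality.

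Much of this stands. A reader might infer that the drug-related table cannot count SOC-related events, or that its SOC column must be zero. The documents do not support that, because the form and the site file decide it. Nor does the SAP itself set related AEs against trial medication; it says only drug-related. No default answer of No is documented.

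It is also fair that the practical reach is limited. Drug-related AEs are not among the safety endpoints in Protocol 5.2.1. Bleeding is centrally adjudicated by a blinded committee, so a bleed on SOC would still appear in the bleeding and AE tables. Changes of SOC with reasons, and discontinuations, are summarised elsewhere (SAP 7.5.2 and 7.7).

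What does not fall away is the conflict itself. Evidence of intent in the analysis sections does not supply data that the collection sections do not ask for.

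**Conclusion.** The point holds as a conflict between a stated collection rule and the analyses planned from it. Followed as written, the rule would bias the descriptive comparison of related AEs against dabigatran. It would also leave the action-taken criterion for other significant AEs undefined for SOC, and the attribution unclear after a switch.

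This rests on reading investigational product and investigational drug as dabigatran, which is how the Protocol uses them, and on sites following that wording.

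The size cannot be established. A reader might be tempted to apply a rate of related AEs to the roughly 47 evaluable SOC patients and report how many would be lost. The documents give no such rate and do not show which reading the form adopts, so the result would only restate the assumptions. It would also be wrong to conclude that the trial's main safety comparison is compromised, since adjudicated bleeding and the all-AE and SAE tables do not use these items.

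**What to change.** - In Protocol 5.2.2.1 and 5.2.2.2, state that relationship and action taken refer to the trial medication received, dabigatran or the SOC anticoagulant.
- In SAP 7.8.1, define drug-related and action taken in the same way, and state which drug each refers to after a switch from dabigatran to SOC, so that the answer matches the period to which the AE is assigned.
- Check the wording of the case report form and the Investigator Site File. Only if they ask about dabigatran alone, query AEs in SOC periods before database lock.

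The cost is a wording change in two documents and a check of two others. If the query is needed, the downside is some site query work; no extra visits or patients are involved.
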